4.2.2 Imaging Key Secondary Efficacy Variable (MR Cohort)

4.2.2.1 Fat Fraction of Vastus Lateralis Muscles assessed by MRS

The key secondary efficacy endpoint relating to imaging data will be the mean change in VL MFF as assessed by MRS before and after 18 months of treatment with givinostat versus placebo. Analysis of this endpoint will only apply to the MR cohort (who will complete magnetic resonance assessment at baseline, 12 and 18 months).

Observed values and change from baseline in VL MFF will be summarised by visit and treatment group for the MR cohort. The listing of MRS data for the final analysis will include the baseline data for all subjects, as well as the post-baseline data for the MR cohort, with a flag to indicate subjects in the MR cohort.

For all analyses of MRS VL MFF, the final results from the blinded review of these data by University of Florida Imaging DMD network (see Section 2.3) will be used (external to the eCRF). The baseline VL MFF value initially entered onto the eCRF, prior to any adjustment from blinded review, will not be used in the analyses and will only be used for the purposes of assignment to target or off-target populations. It is acknowledged that there may be differences between the initial eCRF baseline result and the final baseline result following blinded review. This could mean that the adjusted result indicates the subject is in a different target/off-target population to that assigned from the initial eCRF result. Population assignment will not be adjusted for this. However, the listing of MRS data will include the baseline results from both the eCRF and final blinded data with an indication of the target/off-target outcome in each case.

4.3 Exploratory Efficacy Variables for All Subjects

All exploratory efficacy endpoint data will be listed. The exploratory efficacy variables will be analysed at the final analysis after 18 months of treatment and will be supportive only and not subject to alpha control. Therefore, nominal p-values will be presented with no adjustment.

4.3.1 Time to Run/Walk 10 Metres

Mean change before and after 18 months of treatment with givinostat and placebo in the time to run or walk 10 metres will be assessed. Summary statistics of observed values and change from baseline in the time to run or walk 10 metres will be presented by visit and treatment group. A plot of the average time to run/walk 10 metres at each visit will also be produced by treatment group. A shift table showing the movement of subjects with respect to functional adaptation options (see Appendix 7.3) from baseline to 18 months after treatment will also be presented by treatment group.

Note that where subjects have stopped the test prematurely, this is equivalent to not completing the test and therefore the missing time to run or walk 10 metres will be imputed according to the rules in Section 4.4.4 for summaries, plots and analyses.

Furthermore, in order to additionally assess the time to run or walk 10 metres data in terms of velocity rather than time, a reciprocal transformation will be applied to

convert the timed results to appropriate units of velocity, according to the following conversion:

$$\text{Velocity (metres/second)} = 10 / \text{Completion time (seconds)}$$

where this conversion is applied following any imputation of missing data as described in Section 4.4.4. The summary statistics and plot described above will be repeated for these transformed values. Analysis of this endpoint (described in Section 4.4.2) will also be repeated on the transformed scale.

4.3.2 Paediatric Outcomes Data Collection Instrument (PODCI) Scores

The PODCI quality of life questionnaire can either be completed by the subject's parent or the subject themselves. A total of five subscales (upper extremity function; transfer and basic mobility; sports and physical functioning; pain/comfort and happiness) and one global function scale can be calculated from the questionnaire.

Summary statistics for the raw scores and standardised scores, together with the change from baseline over time for each subscale included in the PODCI assessment, as well as for the standardised scores of the global function scale will be presented by treatment group. These tables will be produced separately for assessments completed by parents and for assessments completed by the subjects themselves. The endpoints of interest will be the change from baseline to 18 months in the standardised scores for each subscale and the global function scale, as completed by the parent and the subject.

Details of the items included in each of the subscales, as well as the calculations to be applied in order to derive the raw and standardised scores, are included in Appendix 7.4.

4.3.3 Percent Predicted 6MWT

The endpoint associated with the % predicted 6MWT is the mean change from baseline to after 18 months of treatment with givinostat or placebo in % predicted 6MWT. The predicted 6MWT at baseline is against healthy male subjects and is calculated using the Geiger formula (Geiger R, 2007) which is given as:

$$\text{♂: } 6\text{MWT} = 196.72 + (39.81 \cdot \text{age}) - (1.36 \cdot \text{age}^2) + (132.28 \cdot \text{height})$$

where age is the re-derived age in years and months at first study drug intake and height is in metres at baseline. The % predicted 6MWT at each visit for a subject is then found as: measurement for 6MWT at the visit / predicted 6MWT at baseline * 100.

Summary statistics of the % predicted 6MWT observed values and change from baseline will be presented by visit and treatment group. In addition, subjects will be assigned to one of two subgroups based on their baseline % predicted 6MWT value (<80% versus ≥80%). A summary table will present the observed values and changes from baseline over time for actual 6MWT values by treatment group and baseline % predicted 6MWT subgroup.

4.3.4 MRI Parameters (MR Cohort Only)

The quantitative analysis of the acquired MRI imaging and QC reviewing will be performed by blinded personnel from University of Florida Imaging DMD. Two QC reviewers will cross-reference the event; in case of disagreement in grading, a third reader will provide independent grading as a tiebreaker.

The following MRI observed values and change from baseline will be summarised by visit and treatment group for the MR cohort. The endpoints of interest will be the mean change from baseline to 18 months in:

- Fat fraction in 5 thigh muscles or muscle groups
 - Vastus lateralis
 - Biceps femoris long head
 - Semitendinosus
 - Quadriceps, encompassing the vastus lateralis, vastus intermedius, vastus medialis, rectus femoris
 - Hamstrings, encompassing the biceps femoris, semitendinosus, semimembranosus.
- Cross-sectional area of 5 thigh muscles or muscle groups
 - Vastus lateralis
 - Biceps femoris long head
 - Semitendinosus
 - Quadriceps, encompassing the vastus lateralis, vastus intermedius, vastus medialis, rectus femoris.
 - Hamstrings, encompassing the biceps femoris, semitendinosus, semimembranosus.
- Fat-corrected cross-sectional area (i.e. contractile CSA) of 5 thigh muscles or muscle groups
 - Vastus lateralis
 - Biceps femoris long head
 - Semitendinosus
 - Quadriceps, encompassing the vastus lateralis, vastus intermedius, vastus medialis, rectus femoris.
 - Hamstrings, encompassing the biceps femoris, semitendinosus, semimembranosus.

The listing of MRI data for the final analysis will include the baseline data for all subjects, as well as the post-baseline data for the MR cohort, with a flag to indicate subjects in the MR cohort.

4.3.5 Time to 10% Persistent Worsening in 6MWT

Time to 10% persistent worsening in 6MWT will be defined as the time from the date of first study treatment to the last time the 6MWT was not $\geq 10\%$ worse than the baseline 6MWT (McDonald, et al., 2013). If a subject has not achieved $\geq 10\%$ persistent worsening in 6MWT, then time to 10% persistent worsening in 6MWT will be censored at the date of the last 6MWT assessment (including imputed assessments per Section 4.4.4.1), i.e. the 18 month assessment.

The number and percentage of subjects who achieved $\geq 10\%$ persistent worsening in 6MWT and of those censored will be summarised by treatment group. The Kaplan-

Meier estimates of the median, 25th percentile and 75th percentile for time to $\geq 10\%$ persistent worsening in 6MWT, together with the associated 2-sided 95% confidence intervals (CI) will also be presented by treatment group. Time to 10% persistent worsening in 6MWT will also be presented graphically by treatment group using a Kaplan-Meier plot.

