#### **9.1.7 Visits 10 – 14 (Weeks 12-60, $\pm$ 7 days)**

The Visits 10, 11, 12, 13 and 14 will respectively happen after 12, 24, 36, 48 and 60 weeks after the Randomization Visit, with a visit window of  $\pm$  7 days.

At Visit 10 – 14 (i.e., every 3 months), the following assessments will be performed unless otherwise noted:

- Collect and record concomitant medications;
- Perform a physical examination;
- Measure vital signs (blood pressure, pulse rate, and body temperature);
- Measure weight;
- Measure height (only at Visits 11 and 13; i.e., after 6 and 12 months of treatment) ;
- Perform a 12-lead ECG (at 2,5 hours  $\pm$ 30 minutes after drug intake);
- Perform pulmonary function tests: FEV1, FVC, FEV1/FVC, and PEF (only at Visit 13);

Pulmonary function as assessed by spirometry at visit 13 should be repeated if the test does not meet ATS/ERS criteria and/or the evaluator deems that a valid attempt to perform a correct maneuver has not been made by the subject.

- Collect blood samples for:
  - hematology;
  - blood chemistry;
  - coagulation tests (PT and aPTT);
- Collect DMD serum biomarkers (only at Visit 13);
- Obtain a urine sample for urine analysis;
- Perform Quality of Life tests (assessed by PODCI) (only at Visit 13; i.e., after 12 months of treatment);
- Perform time to 4SC
- Perform NSAA and 6MWT;
- Perform muscle strength tests;
- Obtain PK blood sample (only at Visits 10, 11, and 13; i.e., after 3, 6, and 12 months of treatment, respectively);

- Dispense and account for study drug;
- Subject diary dispensation and evaluation of drug compliance through diary;
- Assess AEs;
- Perform MRI/MRS evaluation (MR cohort only) (only at Visit 13; i.e., after 12 months of treatment).

At Visit 13, functional tests will be video recorded.

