4 EFFICACY EVALUATION

Unless specified otherwise, all listings will be based on the all enrolled subjects set. All efficacy analyses and summaries will be performed on the ITT analysis set with the exception of analyses and summaries presenting MRI/MRS data which will be on the MR cohort. Additionally, see Section 2.8 regarding use of the target versus overall population.

Baseline is defined as the last non-missing value recorded prior to or on the date of first study treatment. Where the value is recorded on the same date as first study treatment and there is no further information to confirm whether this was prior to start of treatment, the value will be considered prior to treatment if this was a screening or randomisation assessment and will be considered post treatment otherwise.

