4.3.6 Proportion of Subjects with $\geq 10\%$ Persistent Worsening in 6MWT

The proportion of subjects with $\geq 10\%$ persistent worsening in 6MWT at the end of the study (compared to baseline) will be summarised by treatment group. Subjects with $\geq 10\%$ persistent worsening in 6MWT at the end of the study will be defined as those who record a 6MWT value which is $\geq 10\%$ worse than the baseline 6MWT at any visit before or at the end of the study and this remains $\geq 10\%$ worse than baseline until the end of the study.

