4.3.7 Time to Persistent Loss of Standing (Baseline Through End of Study)

Functional assessments are scheduled to take place every 3 months. In order to allow time for recovery due to trauma, a subject will be considered to have persistent loss of standing if they are unable to stand for at least 2 consecutive assessments (i.e. at least 6 months). Start of a persistent loss of standing will be the first assessment where this is observed. A subject is unable to stand if their score for "Rise from floor" on the NSAA assessment is 0b ("Unable") and if their rising from floor grading is 1 on the Rise from floor assessment. If a subject has not met the criteria for persistent loss of standing by the end of the study, the time to persistent loss of standing will be censored at the date of the last NSAA or Rise from floor assessment (including imputed assessments per Section 4.4.4.1), i.e. the 18 month assessment.

The number and percentage of subjects who have persistent loss of standing at any point post-baseline, as well as those censored, will be summarised by treatment group. Time to persistent loss of standing will be calculated as the time from the date of first study treatment to the start of the first occurrence of persistent loss of standing. The Kaplan-Meier estimates of the median, 25th percentile and 75th percentile for time to persistent loss of standing, together with the associated 2-sided 95% CIs will also be presented by treatment group. Time to persistent loss of standing will also be presented graphically by treatment group using a Kaplan-Meier plot.

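### SAP 4.3.5 dates persistent 6MWT worsening at the last event-free visit, so a boy worse from Week 12 onward gets a time of zero or below

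*SAP*

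**What the plan says.** SAP 4.3.5 defines the event time: it "will be defined as the time from the date of first study treatment to the last time the 6MWT was not" at least 10% worse than baseline, and it cites a published natural-history study. A boy without the event "will be censored at the date of the last 6MWT assessment", which the section identifies as the 18-month assessment. Kaplan-Meier quartiles and a plot are planned there, and SAP 4.4.2 adds a Cox model.

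SAP section 4 fixes the other end of the scale: "Baseline is defined as the last non-missing value recorded prior to or on the date of first study treatment".

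SAP 4.3.6 says who has persistent worsening: a value at least 10% worse "at any visit before or at the end of the study and this remains" so until the end.

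The other time-to-event endpoint, loss of standing in SAP 4.3.7, is dated differently: "Start of a persistent loss of standing will be the first assessment where this is observed".

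The SAP gives no rule for a time of zero or below and no reason for the different dating. The SAP addendum adds neither, although its Change 4 revises the loss-of-standing derivation.

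**The concern.** A time-to-event date should mark a point at which the event has happened or been observed. Here it marks a visit at which the event was shown not to have happened. For most boys this only moves the event one visit earlier. For boys who decline fastest, the only good assessment is baseline, so their time is at best zero.

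Negative times are realistic for two reasons:
- Protocol 9.1.2 has study drug dispensed at Visit 3, and Protocol 8.3 describes outpatient administration. No passage found requires the first dose to be taken that day.
- If the Visit 3 6MWT is missing, the baseline rule falls back to the screening test, which Protocol 9.1.1 places 4 weeks (plus or minus 2) before randomisation.

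If such boys are excluded or handled ad hoc after unblinding, the endpoint loses its earliest events. The curve and quartiles would also be read as times to worsening when they are times to the last visit without it.

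**Working it through.** **Visit grid.** SAP 4.3.7 states that "Functional assessments are scheduled to take place every 3 months". Protocol 9.1.7 states that "The Visits 10, 11, 12, 13 and 14 will respectively happen after 12, 24, 36, 48 and 60 weeks after the Randomization Visit", and Protocol 9.1.8 puts the final visit at Week 72. The 6MWT weeks are 0, 12, 24, 36, 48, 60 and 72. Every gap is 12 weeks, which agrees with the SAP's 3 months. SAP 4.4.4.1 imputes missing scheduled assessments, so the grid has no gaps.

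**Both dating rules on that grid**, for a boy who stays worse from the visit shown:

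| First worse at week | Date under SAP 4.3.5 | Date at first worse visit |
|---|---|---|
| 12 | 0 or below | 12 |
| 24 | 12 | 24 |
| 36 | 24 | 36 |
| 48 | 36 | 48 |
| 60 | 48 | 60 |
| 72 | 60 | 72 |

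The difference is 12 weeks each time (12/72 = 17% of follow-up). With the 7-day visit windows it is 84 ± 7 = 77 to 91 days for the first interval, with baseline at Visit 3, and 84 ± 14 = 70 to 98 days for later ones. With the extended 60-day window for the 18-month visit (SAP 2.9), the last interval can be 84 ± 67 = 17 to 151 days.

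**Time for a boy worse from Week 12.** Time = baseline date minus first-dose date, which is at most 0 by the SAP's definition of baseline. It is 0 if both fall on the same day and -1 day if dosing starts the next day. With a fallback to screening and dosing at Week 0, it is -2 to -6 weeks.

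**Share of events affected.** The documents give no event rate, so a constant hazard h per 12-week interval over six visits is assumed. Share at the first visit = h / (1 - (1 - h)^6).
- h = 0.04: 0.04 / 0.217 = 18%
- h = 0.08: 0.08 / 0.394 = 20%

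A constant hazard can never give less than 1/6 (17%). A hazard that rises over time can.

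**Effect on the results.** An illustrative simulation used 74 and 36 boys, constant hazards, assumed placebo 18-month event rates of 30-60%, and an assumed hazard ratio of 0.6 or 1.0.
- Events at time zero: from 4.6 of 25.0 (18%) to 15.5 of 66.3 (23%).
- Cox log hazard ratio: identical under both rules when zero times are kept, because the order of events and censorings is the same.
- Placebo 25th percentile: 12 weeks earlier under the SAP rule (48 against 60, 24 against 36, or 12 against 24, by scenario).
- Dropping the zero-time boys (true ratio 0.6): the median estimated hazard ratio hardly moved, from 0.626 to 0.620 at a 30% placebo rate and from 0.607 to 0.605 at 50%. The loss there is of events, hence precision.
- True onset: on average about 6 weeks after the SAP date and about 6 weeks before the first worse visit.

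**The case against.** The case for leaving the text alone is substantial in several respects.

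- **Neither date is the true onset.** Onset lies between two visits. The SAP date is 0-12 weeks before it and the first-worse date is 0-12 weeks after it. The SAP also cites a source for its choice, which cannot be consulted here. This stands: the 12-week figure holds only against first observation, the convention of SAP 4.3.7.
- **The treatment comparison is intact.** The Cox result is unchanged with zero times kept, and the SAP nowhere says that boys will be dropped. A reader might infer a bias against the drug from losing early placebo events. The documents do not support that, and the simulation shows no such shift under constant hazards.
- **The share rests on an assumption.** Protocol 6.2 expects slower decline in this population, and Protocol 4.2.3 notes natural improvement up to age 7. Both point to a rising hazard and a smaller share.
- **Visit 3 is shared.** Baseline testing and dispensing fall on the same visit, so a negative gap will usually be short. But a short negative time is still unusable.

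Two stronger readings are tempting and do not hold. First, one might infer that events and censorings run on different clocks. Under SAP 4.3.6 persistence must last to the end of study, so a boy without the event is not 10% worse at his last visit, and his censoring date is also his last good assessment. Second, one might infer that a boy worse only at Week 72 is wrongly counted as persistent. SAP 4.3.6 includes the final visit explicitly, this matches the protocol's endpoint of worsening at end of study (Protocol 5.2.5), and SAP 2.7 discloses the wording change.

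None of this supplies a rule for times at or below zero.

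**Conclusion.** The point holds as a defect in one exploratory definition. Applied as written, SAP 4.3.5 gives boys who are worse at Week 12 and at every later visit a time of zero or below, and any negative time cannot be analysed. About 18-20% of events would be affected under a constant hazard of 4-8% per visit, and fewer under a rising hazard. This takes baseline as the last good assessment. If it does not count, these boys have no defined time at all. An unstated convention of adding one day would rescue a same-day zero but not a longer negative gap.

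The Kaplan-Meier curve, and any quantile that is reached, lies 12 weeks before first observation. Not every planned quartile is involved. At the assumed hazards, cumulative events are 1 - 0.96^6 = 22% or 1 - 0.92^6 = 39%, so the median and 75th percentile are not reached, and at 22% neither is the 25th.

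The Cox hazard ratio is unaffected if zero times are kept and no time is negative. SAP 4.3 makes exploratory endpoints supportive with nominal p-values, so no primary or key secondary conclusion changes.

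**What to change.** In SAP 4.3.5, define the event date as the first visit of the unbroken run of assessments at least 10% worse than baseline that lasts to the end of study. Keep censoring at the last 6MWT. Event times then fall at the scheduled Weeks 12 to 72, none is at or below zero, and the dating agrees with SAP 4.3.7.

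The cost is one sentence and trivial programming, with no new data. The downside is small: dates then fall 0-12 weeks after true onset and depart from the cited published definition. That definition can be kept as a sensitivity analysis, with a stated rule for times at or below zero.

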4.3.6 Proportion of Subjects with $\geq 10\%$ Persistent Worsening in 6MWT

The proportion of subjects with $\geq 10\%$ persistent worsening in 6MWT at the end of the study (compared to baseline) will be summarised by treatment group. Subjects with $\geq 10\%$ persistent worsening in 6MWT at the end of the study will be defined as those who record a 6MWT value which is $\geq 10\%$ worse than the baseline 6MWT at any visit before or at the end of the study and this remains $\geq 10\%$ worse than baseline until the end of the study.

4.3.7 Time to Persistent Loss of Standing (Baseline Through End of Study)

Functional assessments are scheduled to take place every 3 months. In order to allow time for recovery due to trauma, a subject will be considered to have persistent loss of standing if they are unable to stand for at least 2 consecutive assessments (i.e. at least 6 months). Start of a persistent loss of standing will be the first assessment where this is observed. A subject is unable to stand if their score for "Rise from floor" on the NSAA assessment is 0b ("Unable") and if their rising from floor grading is 1 on the Rise from floor assessment. If a subject has not met the criteria for persistent loss of standing by the end of the study, the time to persistent loss of standing will be censored at the date of the last NSAA or Rise from floor assessment (including imputed assessments per Section 4.4.4.1), i.e. the 18 month assessment.

The number and percentage of subjects who have persistent loss of standing at any point post-baseline, as well as those censored, will be summarised by treatment group. Time to persistent loss of standing will be calculated as the time from the date of first study treatment to the start of the first occurrence of persistent loss of standing. The Kaplan-Meier estimates of the median, 25th percentile and 75th percentile for time to persistent loss of standing, together with the associated 2-sided 95% CIs will also be presented by treatment group. Time to persistent loss of standing will also be presented graphically by treatment group using a Kaplan-Meier plot.

4.3.8 Proportion of Subjects Who Lose Ambulation

The proportion of subjects who lose ambulation during the study will be summarised by treatment group. Loss of ambulation is defined as any subject who satisfies both of the following criteria at the same visit at any point prior to or at the end of the study and continues to satisfy the criteria at all subsequent visits to the end of the study:

- Subject is unable to perform the 6MWT due to physical inability
- Subject is unable to complete the 10-metre walk/run test in 30 seconds or less without any support or devices (10-metre walk/run test grading ≤ 2).

4.3.9 Correlation between the effect of Givinostat on disease progression and the type of DMD mutation, LTBP4 and Osteopontin genotype

The exploratory endpoint of interest here is to evaluate any correlation between the effect of givinostat on disease progression and separately: the type of DMD mutation (Deletion, Duplication, Point Mutation); LTBP4 genotype (VTTT, IAAM, Other); Osteopontin (SPP1) genotype (TT, GT, GG). This will be evaluated via summaries, plots and analyses for these subgroups of subjects, as described in Section 4.4.6. If deemed of interest, additional investigation into correlation between these subgroups and the effect of givinostat on disease progression may be included at a later date as post hoc analyses.

